## **Comparison between single shot versus continuous infraclavicular brachial plexus block for postoperative analgesia after distal radius fracture, a prospective randomized open label study**

Pain control following fracture surgery is closely associated with overall patient satisfaction (1). Systemic analgesia (intravenous or oral) are not site specific and may be associated with undesirable side effects such as nausea, constipation, and pruritus. Peripheral blocks provide not only intraoperative anesthesia and pain control but also offer the advantage of lasting analgesic effect into the post-operative period. However, as these blocks wear off, some patients experience a high level of pain. This "rebound phenomenon" has been described and is considered by some authors as one of the shortcoming of single shot peripheral nerve blocks in multiple orthopedic surgical settings (2). Extension of the analgesic benefits of the peripheral nerve blocks can be achieved in the ambulatory settings using continuous perineural ambulatory catheters (3). Use of regional anesthesia for repair of distal radius fracture has been associated with improved pain scores and improved functional outcomes when compared to general anesthesia (4). The impact of extension of these benefits in the settings of distal radius fractures on patient satisfaction, the quality of pain management, quality of recovery, and functional outcome is not entirely known. This study aims to compare the effect of single shot infraclavicular brachial plexus blocks to continuous peripheral nerve blocks on pain scores after surgery.

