### **Study Objectives:**

- 1- Measure visual analogue scores every 8 hours for 72 hours after surgery. Pain scores will be recorded by patients in a pain diary (see appendix)
- 2- Measure opioid requirements for the first 3 days after surgery
- 3- Measure patient satisfaction with their pain management.
- 4- Measure the quality of recovery (QOR) at 24 and 72 hours. using the QOR-9 questionnaire.( see appendix)
- 5- Measure the quality of sleep in the first two nights after surgery using a sleep questionnaire ( see appendix)
- 6- Functional outcomes will be assessed at 3 months follow up during the office visit or through administration of the disability assessment of shoulder and hand questionnaire, range of motion of the wrist and fingers will be recorded. (see appendix)

This study tests the hypothesis that patients receiving continuous ICB will have lower pain scores, will use less opioids, will sleep better the first two nights after surgery and will be more satisfied with their pain control regimen after surgery.

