Block success will be defined as a change in cutaneous sensation to touch with an alcohol pad in the posterior, medial and lateral cord distribution over the forearm and the hand within 30min after injection. Subjects with successful catheter placement per protocol and nerve block onset will be retained in the study. Subjects with a failed catheter insertion or misplaced catheter indicated by a lack of sensory changes will have their catheter replaced or will be single shot blocked and withdrawn from the study.

Intraoperative sedation will consist of intermittent boluses of midazolam (1-2 mg), fentanyl (50-100 mcg) and propofol infusion, titrates to sedation and patient comfort (25-50 mcg/kg/min).

All patients will receive prophylaxis for postoperative nausea and vomiting (PONV) during surgery. The protocol for prophylaxis against PONV includes administration of 4 mg of dexamethasone after induction of anesthesia and 4 mg of ondansetron 20 minutes before recovery from anesthesia. Dexamethasone is withheld if the patient has poorly controlled diabetes mellitus (DM). Uncontrolled DM will be defined as random blood glucose above 250 mg/dl

**Protocol for postoperative analgesia:** At the conclusion of surgery, the catheters will be connected to a pump that will infuse local anesthetic. Ropivacaine 0.2% at a basal rate of 5 ml/hour and a patient administered on demand bolus of 5 ml with lock out interval every 60 minutes. In the PACU, intermittent boluses of hydromorphone will be used as needed. Postoperative analgesia will follow the current oral prescription protocol. Drugs that are used for postoperative analgesia include oxycodone/acetaminophen (5/325 mg) one to two tablets every four to 6 hours as needed by the patient with oxycodone 5-10 mg oxycodone oral tablets every 4 hours as needed for break through pain.

Patients will be followed up daily by the acute pain service resident as per our routine clinical practice for follow up for ambulatory perineural catheters. Patients will take out the catheter themselves at home as per protocol.

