#### **Measurements:**

- 1- Visual analogue scores every 8 hours for 72 hours after surgery. Pain scores will be recorded by patients in a pain diary
- 2- Measure opioid requirements for the first 3 days after surgery
- 3- Measure patient satisfaction with their pain management.
- 4- Measure the quality of recovery at 24 and 72 hours
- 5- Measure the quality of sleep in the first two nights after surgery. sleep quality questionnaire is adapted from the insomnia severity index (6) and we added

another questions asking about the frequency of waking up at night because of pain after surgery (7, 8)

6- Functional outcomes will be assessed at 3 months follow up during the office visit or through administration of the quick disability assessment of shoulder and hand (DASH) questionnaire (9), range of motion of the wrist and fingers will be recorded.

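### No opioid side effect, block or catheter complication, or nerve symptom is a planned outcome, although one arm goes home with a ropivacaine catheter

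*Combined protocol and SAP*

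**What the plan says.** The combined protocol and SAP lists the same six items under Study Objectives and under Measurements:

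1. Pain: "Visual analogue scores every 8 hours for 72 hours after surgery", kept by the patient in a diary.
2. Opioid use: "Measure opioid requirements for the first 3 days after surgery".
3. Satisfaction: "Measure patient satisfaction with their pain management".
4. Recovery: "Measure the quality of recovery at 24 and 72 hours", using the QOR-9.
5. Sleep on the first two nights.
6. Function at three months: the quick DASH, with wrist and finger motion.

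The hypothesis under Study Objectives is that "patients receiving continuous ICB will have lower pain scores, will use less opioids, will sleep better the first two nights after surgery", with greater satisfaction. The Statistical Analysis section covers demographic data, pain scores and categorical data in general, and names no safety analysis.

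Under the postoperative analgesia protocol, the continuous arm receives "Ropivacaine 0.2% at a basal rate of 5 ml/hour and a patient administered on demand bolus of 5 ml with lock out interval every 60" (the interval is in minutes), and "Patients will take out the catheter themselves at home as per protocol". The same part of the protocol provides daily follow-up by the acute pain service, described as the routine for ambulatory catheters. A failed or misplaced catheter is replaced, or the patient has a single-shot block and leaves the study. The background says that systemic analgesics "may be associated with undesirable side effects such as nausea, constipation, and pruritus".

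**The concern.** The two arms differ by an added invasive device that is used and removed at home. The burdens that could offset its benefit are leakage, dislodgement, infection, local anesthetic symptoms, difficult removal, unplanned contacts and nerve symptoms. The effects that less opioid might spare are nausea, constipation and pruritus. None of these is a planned outcome in either arm.

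The trial could then report lower pain and better satisfaction with nothing collected on equal terms to set against them. Analysts cannot repair this afterwards, because events not asked about at the time cannot be recovered reliably. Notes from the pain service would not fill the gap either. They would exist mainly for catheter patients, so the arm that is watched more closely could appear to have more harm.

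**Working it through.** **Coverage.** Pain, opioid amount, satisfaction, quality of recovery, sleep and three-month function were each read against three kinds of harm: opioid side effect, block or catheter complication, and nerve symptom. Named harm outcomes: 0 of 6, under both Study Objectives and Measurements. Safety analyses under Statistical Analysis: 0.

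**Other places where harm might be picked up.**
- Daily follow-up: no form, data item or analysis is attached, and nothing equivalent is described for the single-shot arm.
- Catheter failure: this leads to replacement or withdrawal. It is not an outcome.
- Appendix forms: not shown, so their items are unknown.

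**Numbers available.** Recruitment gives 25 patients per arm. Sample Size Calculation gives 38 evaluable patients, 20% dropout and 50 enrolled. Check: 38/(1 − 0.20) = 47.5, so 48, which agrees with 50 to within 2 patients. With 20% dropout in each arm, 25 × 0.80 = 20 remain.

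**What zero events would show.** One-sided 95% upper bound = 1 − 0.05^(1/n).
- n = 25: 1 − 0.05^(1/25) = 11.3%
- n = 20: 1 − 0.05^(1/20) = 13.9%

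The upper limit of a two-sided 95% exact interval is 1 − 0.025^(1/n), which gives 13.7% and 16.8%.

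**Chance of seeing at least one event** = 1 − (1 − p)^n. For example, at p = 0.05 and n = 25, 1 − 0.95^25 = 0.723. The documents give no event rates, so every rate below is an assumption.

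| Assumed true rate | n = 25 | n = 20 |
|---|---|---|
| 1% | 22% | 18% |
| 2% | 40% | 33% |
| 5% | 72% | 64% |
| 10% | 93% | 88% |
| 20% | 99.6% | 99% |

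**Could a common side effect be compared formally?** The check is a two-sided 5% test of two proportions by normal approximation: power = Φ{[|p1 − p2| − 1.96√(2p̄(1 − p̄)/n)] / √[(p1(1 − p1) + p2(1 − p2))/n]}, where p̄ is the mean of p1 and p2. For an assumed 40% versus 20% with n = 25 per arm, this is Φ[(0.20 − 1.96 × 0.1296)/0.1265], or 33%. For 50% versus 20% it is 61%, and for 40% versus 10% it is 70%. With 20 per arm the three values fall to 28%, 51% and 60%. Recording would support description by arm, not a powered comparison.

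**The case against.** Four stronger readings are tempting, and the documents do not support them.

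- *The trial can show only benefit.* Quality of recovery, satisfaction, sleep, quick DASH and range of motion can each favour either arm, and a lasting deficit could appear as worse function. What is missing is any outcome that identifies a harm as such.
- *The plan yields no harm data at all.* The diary, QOR-9, sleep and DASH forms sit in an appendix that is not shown, so symptom items cannot be ruled out. The daily follow-up may also detect complications clinically, and withdrawals for initial catheter failure would be identifiable. None of this is a planned outcome.
- *The trial leaves its own rationale untested.* The background sentence on side effects contrasts systemic analgesia with nerve blocks in general, and both arms here receive a block. The argument for the continuous technique is that single-shot blocks wear off. The hypothesis claims less opioid use, not fewer side effects.
- *A three-month symptom question would separate block injury from fracture or surgical injury.* In an individual patient it would not. Only the comparison of randomised arms is interpretable.

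It can also be objected that the trial is too small for safety. In part this stands: at true rates of 1% to 2%, 25 patients would more often than not show no event, and a powered comparison is out of reach. It does not defeat the point for commoner problems, where counts with intervals are informative.

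**Conclusion.** The omission is real and worth correcting. No listed outcome is an opioid side effect, a block or catheter complication or a nerve symptom, and no safety analysis is planned, while one arm carries an additional home catheter and infusion. The only described contact that might detect complications has no stated data capture and is described for catheters, so harms found through it would be ascertained unequally. A benefit on pain, opioid use or satisfaction could not be weighed against harms measured the same way in both arms.

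In size, what is lost is modest but useful: a bound of 11.3% to 13.9% if no event is seen, and a 64% to 72% chance of seeing at least one event if the true rate is 5%. These figures assume independent patients, complete recording, 20 to 25 patients per arm and, for the second, an assumed rate. The conclusion itself rests on the text and on none of these numbers. It is limited to planned outcomes, because the appendix forms could not be read.

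**What to change.** Add a seventh measurement to Study Objectives and Measurements:

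- **(a) Diary checklist.** In the existing 72-hour diary, yes/no items with the same questions and times in both arms: nausea or vomiting, pruritus, constipation, local anesthetic symptoms, and unplanned calls or visits. For the continuous arm only, add leak, dislodgement, redness and difficult removal.
- **(b) Failure count.** By randomised arm, count block failures, catheter replacements and the withdrawals that follow catheter failure.
- **(c) Three-month question.** At the planned follow-up, ask about new numbness, tingling or weakness in the operated limb. Compare by randomised arm without attributing individual cases to the block.

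In Statistical Analysis, state that these will be reported as counts per arm with exact confidence intervals, as description. Any conclusion about the continuous block should cite them. If the appendix forms already hold some of these items, name those items as outcomes instead of asking twice.

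The cost is one extra diary page, one extra question, a little more patient burden and some data entry. No visit, procedure or clinical rule changes.
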